### ***Validity assessment***

Validity refers to an instrument measures exactly what it proposes to measure. Validity can be assessed in different forms such as content validity, convergent validity, criterion validity, and construct validity. **Content validity** can be defined as the extent to which an assessment tool accurately and fully reflects the concept being measured. The Delphi technique will be used to establish the content validity of the P-CIN. We will obtain the opinions of 10 experts through a structured questionnaires delivered two iterations until consensus will be reached. **Convergent validity** is the degree to which scores on a measure associate with scores on other measures that are intended assess similar constructs. Pain level, self-reported quality of life are CIPN-related concepts that have been identify pediatric oncology patients with CIPN risk[15]. Therefore, convergent validity will be explored using well-established CIPN-related measurements, namely, (1) the Wong-baker FACES pain rating scale to assess levels of pain; and (2) the Pediatric Quality of Life Inventory (PedsQL) Cancer Module to determine level of quality of life with the help of the Spearman's correlation coefficient (r). **Criterion validity** is the relation between the score of a certain instrument and some external criterion. This criterion has to be a widely accepted measure, with the same characteristics of the assessment tool. Criterion validity will be evaluated using the pediatric neurologists' CIPN diagnosis as a reference criterion. Spearman's correlation coefficient (r) will be calculated to evaluate the correlations between the P-CIN and the CIPN diagnosis. Using diagnostic testing to determine the presence or absence of the CIPN is essential. The ROC curve aims to find an optimal cut-off value with the best CIPN diagnostic performance. Additionally, the ROC curve is utilized to evaluate the overall diagnostic performance of a test and to compare multiple diagnostic tests.[23] The area under the curve (AUC) will be used to measure the accuracy of diagnostic test. Generally, an  $AUC \geq 0.8$  is considered acceptable. Youden statistic (calculated as sensitivity + specificity - 1) was used to determine the optimal cut-off value.[24] The point at which this value is maximized is determined as the optimal cut-off value.[24]

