## **Sample size**

Although there is no golden standard for the sample size calculation for validation study in nursing research, the recommended sample size for factor analyses is between 150 to 180.[7] In addition, the Exploratory Factor Analysis (EFA) and Confirmatory Factor Analysis (CFA) must be conducted on different datasets.[8] We therefore determined to recruit 300 pediatric oncology patients in our validation study.

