### ***Factor analysis***

Factor analysis is valuable for evaluating sampling adequacy, internal consistency, factor rotation, factor identification, item retention, and other analytical processes. Exploratory Factor Analysis (EFA) and Confirmatory Factor Analysis (CFA) are two common techniques used in scale adaptation studies. EFA will be conducted to determine the number of underling latent factors and the structure of items. Following the execution of the EFA, a measurement model will be applied to examine CFA using three critical results: parameter estimates, fit indices, and modification indices. In our study, the sample will be randomly

split into two halves (half for EFA and half for CFA).

EFA will be performed by using the SPSS software, version 29.0 for Mac (SPSS Inc., Chicago, IL, United States). Suitability of the matrix for conducting the EFA will test using the Kaiser-Meyer-Olkin (KMO) test and Bartlett's test of sphericity. The KMO sampling adequacy test will be deemed adequate if the value was greater than 0.6. A significant level of  $P$ -value  $< 0.05$  of Bartlett's Test of Sphericity indicates EFA can be performed. The number of factors that should be retained in the model was determined using eigenvalues and scree-plot. All factors with eigenvalues above one was retained according to the Kaiser's criteria. In addition, factors corresponding to data points lying above the point of inflexion of the scree-plot were also retained. Principal component analysis will be performed to conduct an additional factor analysis, which helps determine the loadings for every factor selected. Analyze the factor composition and the factor loading of each item on the corresponding factor, and delete items with factor loading  $< 0.50$ . Cumulative variance contribution rate be above 50%. We will apply the varimax type of rotation. In addition, varimax rotation will be chosen since it minimizes factor complexity while, at the same time, maximizing the variance of factor loadings.

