good discrimination, 0.4 and above indicate very good discrimination. Good internal consistency reliability is indicated by a Cronbach's alpha coefficient  $\geq 0.70$  and item-total score correlations ranging from 0.30 to 0.70. The intraclass correlation coefficient (ICC) will be used to evaluate the **test-retest reliability**. For the results interpretation, minimum ICC values of 0.70 are considered satisfactory, values above 0.8 or 0.9 are often regarded as a sign of good or excellent test-retest reliability.[26] Concerning for the **content validity**, a scale with excellent content validity should be composed of I-CVIs of 0.78 or higher and UA -CVI/Ave-CVI of 0.8 and 0.9 or higher, respectively. Spearman's correlation coefficient ( $r$ ) will be performed to evaluate **convergent validity**. The correlation values for convergent validity are classified as follows:  $r=0$ , no correlation;  $r=0.10-0.29$  ( $-0.10$  to  $-0.29$ ), negligible correlation;  $r=0.30-0.49$  ( $-0.30$  to  $-0.49$ ), low positive (negative) correlation;  $r=0.50-0.69$  ( $-0.50$  to  $-0.69$ ), moderate positive (negative) correlation;  $r=0.70-0.89$  ( $-0.70$  to  $-0.89$ ), high positive (negative) correlation;  $r=0.90-1.00$  ( $-0.90$  to  $-1.00$ ), very high positive (negative) correlation.[27] Spearman's correlation coefficients equal to 0.70 or over are desirable. To determine **criterion validity**, Spearman's correlation coefficient will be used. Concerning the effectiveness diagnostic test, receiver operating characteristic (**ROC**) curve analysis will be performed. The interpretation of the **AUC** as follows: fail ( $0.5 \leq \text{AUC} < 0.6$ ), poor ( $0.6 \leq \text{AUC} < 0.7$ ), fair ( $0.7 \leq \text{AUC} < 0.8$ ), good ( $0.8 \leq \text{AUC} < 0.9$ ), excellent ( $0.9 \leq \text{AUC}$ ). **Youden's Index** will be used to calculate the optimal cut-off value. Concerning the CFA,  $\chi^2/\text{df}$  for value lower than 5 the fit is acceptable. RMR and SRMR: the lower the values, the better the fit. GFI and CFI values over 0.90 are considered a good fit (with a maximum value equal to 1). Reference value for the RMSEA between 0.05 to 0.08 mean the adjustment is good. Factor loading values above or close to 0.70 are better to explain the structure. As for the clinical feasibility, the P-CIN will be considered a practical tool for implementation in clinical practice settings if 80% or more of the children completed the questionnaire independently.

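### The Youden cut-off is picked in the one cohort of 300 with no internal validation, so any accuracy quoted at that cut-off will be overstated on average.

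*Protocol*

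**What the plan says.** Criterion validity is assessed against the pediatric neurologists' CIPN diagnosis. On the purpose of the ROC analysis, the Protocol (Validity assessment) says: "The ROC curve aims to find an optimal cut-off value with the best CIPN diagnostic performance". The rule for choosing the cut-off is the maximum of sensitivity plus specificity minus 1: "The point at which this value is maximized is determined as the optimal cut-off value". The Data analysis section repeats that Youden's index "will be used to calculate the optimal cut-off value" and adds no further step.

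The accuracy measure is named separately: "The area under the curve (AUC) will be used to measure the accuracy of diagnostic test". The AUC has a threshold (0.8 or above is acceptable) and interpretation bands. Sensitivity and specificity have neither.

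On the sample, the Sample size section says: "We therefore determined to recruit 300 pediatric oncology patients in our validation study". Its stated basis is that "the recommended sample size for factor analyses is between 150 to 180" and that "the Exploratory Factor Analysis (EFA) and Confirmatory Factor Analysis (CFA) must be conducted on different datasets". The Factor analysis section then has the sample "split into two halves (half for EFA and half for CFA". No other division of the sample, resampling step or separate cohort is described for the ROC analysis.

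**The concern.** P-CIN totals run from 0 to 65, so the rule searches up to 66 candidate values for the highest point of an empirical curve. That curve contains sampling noise. Its maximum tends to fall where the noise is favourable, so the J observed there exceeds, on average, the J which the same cut-off would have in new children. The chosen score also varies from sample to sample.

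At stake are the figures attached to the cut-off. The background section promotes the P-CIN for early identification of CIPN. If sensitivity at the cut-off is quoted too high, more affected children would be missed than a reader expects. The effect grows as cases become fewer. The reference diagnosis needs abnormal nerve conduction in two or more nerves, a CTCAE score of at least 2 and a supporting clinical consultation, all together. A small number of cases is therefore plausible, though the protocol does not give one.

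**Working it through.** **1. The plan's own figure.** Two separate factor-analysis samples at the lower recommended bound give 2 × 150 = 300, which matches the stated total. (The upper bound would give 2 × 180 = 360.) The total is thus explained by factor analysis. No number of cases, sensitivity or specificity is stated for the ROC analysis, so there is no ROC figure to reproduce.

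**2. Inputs.** From the Protocol: N = 300; integer score 0 to 65; cut-off at the maximum of J = sensitivity + specificity − 1. Assumed, because the Protocol does not give them: true AUC of 0.7, 0.8 or 0.9; 3% to 50% of children meeting the reference diagnosis; and an equal-variance binormal score, with a right-skewed variant as a check. The Protocol's background quotes an incidence of 2.8% to 100% depending on the measure, which does not narrow the range.

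**3. Best attainable J at AUC 0.8.** For the binormal score, the separation is d = √2 × Φ⁻¹(0.8) = 1.19. The best J is 2Φ(d/2) − 1 = 2 × 0.724 − 1 = 0.448.

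**4. Simulation.** In each of 4,000 simulated studies per setting, the Youden cut-off was chosen in the sample, and its apparent values were compared with the true values of that same cut-off. Overstatement = apparent J − true J. Results at AUC 0.8, N = 300:

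| CIPN cases | Apparent J | True J | Overstatement of J | Of which sensitivity | Of which specificity |
|---|---|---|---|---|---|
| 150 | 0.470 | 0.437 | 0.033 | 1.5 points | 1.8 points |
| 90 | 0.472 | 0.436 | 0.036 | 2.5 points | 1.1 points |
| 60 | 0.477 | 0.435 | 0.042 | 3.5 points | 0.7 points |
| 30 | 0.494 | 0.429 | 0.065 | 5.9 points | 0.6 points |
| 15 | 0.522 | 0.420 | 0.102 | 9.8 points | 0.4 points |

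The skewed score gave similar values (0.063 with 30 cases, 0.030 with 150). Over AUC 0.7 to 0.9 and 5% to 50% prevalence, the average overstatement of J ran from about 0.026 to 0.113. J was overstated in about 73% to 87% of samples, so not in all of them.

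**5. Does the remedy work?** Bootstrap optimism correction was tried at AUC 0.8 (200 resamples, 300 simulated studies):

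- 30 cases: apparent 0.493, corrected 0.445, true 0.429. Share removed: (0.493 − 0.445)/(0.493 − 0.429) = 0.048/0.064 = 75%.
- 90 cases: apparent 0.472, corrected 0.444, true 0.437. Share removed: 0.028/0.035 = 80%.

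**The case against.** The strongest reply has four parts.

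**Reporting.** The Protocol never says that sensitivity and specificity at the cut-off will be reported or used as evidence of validity. They appear only inside the Youden formula, and accuracy is to be judged by the AUC. This stands. A reader might infer that the plan commits to publishing inflated accuracy at the maximised point, but the text does not go that far. The point concerns any such figure that is quoted. The stated aim of a best-performing cut-off makes that likely but does not promise it.

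**Consistency.** A reader might infer that the sample was split for factor analysis in order to avoid this same bias, so that the Protocol contradicts itself on the ROC. It gives no motive for the split beyond a citation. All that can be said is that data are separated for one exploratory step and not for the other.

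**Size.** With sensitivity and specificity both near 0.72, the binomial standard error of J is √[0.72 × 0.28 × (1/cases + 1/non-cases)]. That is 0.052 with 150 cases, 0.057 with 90, 0.065 with 60 and 0.086 with 30. The overstatement is below one standard error in each of these settings. This also stands, and it limits the weight of the point. It does not remove it: sampling error can fall either way, whereas this bias has a known direction and can largely be corrected.

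**Level of detail.** Internal validation could sit in a statistical analysis plan that is not at hand. That is possible. But the Protocol itself fixes the selection rule and treats its result as the optimal value, with no provisional status, so the consequence of following that rule can fairly be raised here.

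**Conclusion.** The concern holds as a cheap improvement. Following the stated rule in the single cohort gives a cut-off whose apparent sensitivity, specificity and J are optimistic on average. With 300 children and an assumed true AUC of 0.8, the average overstatement of J is about 0.03 to 0.04 with 60 to 150 cases and about 0.06 with 30 cases, mostly in sensitivity when cases are few. These sizes rest on the assumed AUC, score shape and number of cases. The number of cases matters most, and the Protocol does not state it.

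Two further readings are not supported. The full-score AUC does not depend on which cut-off is chosen, so this issue does not bias the Protocol's stated accuracy measure or its 0.8 threshold. Nor does the Youden rule itself need replacing: what is missing is a correction for having searched for the maximum.

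**What to change.** Keep the Youden rule and use all 300 children. Add to the Data analysis section that the full cut-off selection will be repeated in bootstrap resamples (for example 1,000). Any sensitivity, specificity and J given at the cut-off should be optimism-corrected, with 95% confidence intervals. A bootstrap interval for the cut-off itself should be given, together with the number of children who meet the reference diagnosis. Describe the cut-off as provisional until it has been tested in new children.

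Choosing the cut-off in one half of 150 and testing it in the other would also avoid the bias, but the cut-off would be less stable, so the bootstrap is preferable here.

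The cost is a little more analysis and slightly less favourable reported accuracy. No extra patients are needed.

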### ***Factor analysis***

Factor analysis is valuable for evaluating sampling adequacy, internal consistency, factor rotation, factor identification, item retention, and other analytical processes. Exploratory Factor Analysis (EFA) and Confirmatory Factor Analysis (CFA) are two common techniques used in scale adaptation studies. EFA will be conducted to determine the number of underling latent factors and the structure of items. Following the execution of the EFA, a measurement model will be applied to examine CFA using three critical results: parameter estimates, fit indices, and modification indices. In our study, the sample will be randomly

split into two halves (half for EFA and half for CFA).

EFA will be performed by using the SPSS software, version 29.0 for Mac (SPSS Inc., Chicago, IL, United States). Suitability of the matrix for conducting the EFA will test using the Kaiser-Meyer-Olkin (KMO) test and Bartlett's test of sphericity. The KMO sampling adequacy test will be deemed adequate if the value was greater than 0.6. A significant level of  $P$ -value  $< 0.05$  of Bartlett's Test of Sphericity indicates EFA can be performed. The number of factors that should be retained in the model was determined using eigenvalues and scree-plot. All factors with eigenvalues above one was retained according to the Kaiser's criteria. In addition, factors corresponding to data points lying above the point of inflexion of the scree-plot were also retained. Principal component analysis will be performed to conduct an additional factor analysis, which helps determine the loadings for every factor selected. Analyze the factor composition and the factor loading of each item on the corresponding factor, and delete items with factor loading  $< 0.50$ . Cumulative variance contribution rate be above 50%. We will apply the varimax type of rotation. In addition, varimax rotation will be chosen since it minimizes factor complexity while, at the same time, maximizing the variance of factor loadings.

Following the execution of the EFA, CFA will be accomplished using IBM SPSS Amos, version 29.0. CFA will be used to establish and validate the construct validity of the P-CIN. Maximum Likelihood was used as the estimation method. To evaluate the goodness of fit, the following statistical measures will be utilized: ratio of chi-square and degrees of freedom ( $\chi^2/df$ ), root mean square residual (RMR), standardized root mean square residual (SRMR), goodness of fit index (GFI), comparative fit index (CFI), root mean square error of approximation (RMSEA).

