The original P-CIN was developed in 2021 and the first electronic CIPN patient reported outcome measure (PROM). The European Organisation for Research and Treatment of Cancer Quality of Life Questionnaire - Chemotherapy-Induced Peripheral Neuropathy 20-item sub-scale (EORTC QLQ-CIPN20) served as a model when developing P-CIN specific items, and further validated in pediatric patients with CIPN in the United States. The P-CIN contains four items to rate CIPN subjective symptoms - numbness and tingling in the hands and feet. If pediatric patients reported experiencing these symptoms, they were directed to answer four additional questions regarding painful numbness and tingling. Five items were used to quantify CIPN functional deficits experienced such as picking up a penny or heel-

walking. Evidence indicates that the P-CIN is reliable and valid in United States context. However, there is a lack of measures for CIPN assessment in China after a systematic search and the P-CIN has never been validated for use with pediatric patients with CIPN in China. This lack of validated assessment measures preclude understanding the severity of the CIPN and hinders the development of appropriate interventions to promote CIPN symptoms management. On the other hand, a culturally sensitive assessment is critical in defining, identifying, describing and understanding the signs and symptoms of CIPN[3] as the culture and language can impact the expression and interpretation of symptom characteristics.[4] For instance, in East Asia, terms like “burning” were never used, with patients may report “numbness”.[4, 5] Due to the aforementioned concerns, it may be not appropriate to apply the P-CIN to assess the CIPN severity of pediatric patients before cross-cultural adaptation and validation. It is essential that assessment measures are appropriately adapted and validated in a new cultural setting to ensure valid and reliable measures.

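### At 150 children the eigenvalue-above-one rule may keep too many factors, nothing else in the plan lowers the count, and the P-CIN's own groupings are not named as CFA models

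*Protocol*

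**What the plan says.** Two retention rules stand in the Factor analysis section. The first is Kaiser's: "All factors with eigenvalues above one was retained". The second is joined to it as an addition: "factors corresponding to data points lying above the point of inflexion of the scree-plot were also retained". The section's other criteria do different work. The KMO and Bartlett checks decide whether an exploratory factor analysis (EFA) may be run. The cumulative-variance requirement of 50% is a floor. The 0.50 cut is an instruction to "delete items with factor loading" below that value, so it acts on items.

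The Sample size section sets 300 children, and the Factor analysis section divides them at random into equal halves for the EFA and the confirmatory factor analysis (CFA). The order is fixed: "Following the execution of the EFA, a measurement model will be applied to examine CFA using three critical results".

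The protocol also describes the structure of the original form in two ways. The P-CIN paragraph under CIPN measurements counts eight symptom items and five function items. Section 4 (Scope and Background of Research) divides the eight further: "The P-CIN contains four items to rate CIPN subjective symptoms", followed by four on painful numbness and tingling, then five on function. Neither grouping is named as a model for the CFA.

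**The concern.** A retention procedure needs something that can stop it. Here the scree plot may add a factor but never remove one, so the eigenvalue count is a minimum. That rule tends to keep too many factors when the sample is moderate, loadings are modest, or items pile up at 0. Many zeros are plausible, because the Participants section requires exposure to neurotoxic drugs and not neuropathy.

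The EFA is meant to settle how many factors there are and which items belong to each, and the CFA follows from it. If the EFA keeps a spurious factor, the model sent to the second half has items in the wrong groups, and the construct-validity result is about that model. The structures that the protocol itself describes might never be tested.

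**Working it through.** **Inputs from the protocol.** Total 300 (Sample size); random halves (Factor analysis), so 300 / 2 = 150 for the EFA. The 300 agrees with twice the lower end of the quoted range of 150 to 180: 2 × 150 = 300. There are 13 items on a 6-point scale with total 0 to 65 (CIPN measurements), so items run 0 to 5, since 13 × 5 = 65. Data analysis prefers loadings near or above 0.70.

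**Assumed, because the protocol does not give them.** Equal loadings of 0.6, 0.7 or 0.8; endorsement (share scoring above 0 on an item) of 20, 30, 50 or 70%, with positive scores spread evenly over 1 to 5; Pearson correlations; every child answers all 13 items. Section 4 cites CIPN incidence from 2.8% to 100%, which does not narrow endorsement.

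**Why the rule can fail.** Take two factors (8 + 5 items), loading 0.6 and factor correlation 0.6, with continuous items and unlimited data. Within-group correlations are 0.6² = 0.36 and between-group correlations 0.36 × 0.6 = 0.216. The two real eigenvalues come from a 2 × 2 matrix with diagonal 1 + 7 × 0.36 = 3.52 and 1 + 4 × 0.36 = 2.44, and off-diagonal 0.216 × √40 = 1.366. They are 2.98 ± √(0.54² + 1.366²) = 4.45 and 1.51. The other eleven equal 1 − 0.36 = 0.64. (Check: 4.45 + 1.51 + 11 × 0.64 = 13.0.) So the rule is right in the limit. At n = 150 sampling error spreads those eleven upward, and coarse items with many zeros weaken the correlations and push them closer to 1. At loadings 0.7 and 0.8 they start lower, at 1 − 0.49 = 0.51 and 1 − 0.64 = 0.36.

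**Simulation, n = 150, two true factors (8 + 5, correlation 0.6), 1000 data sets per cell.** Share keeping three or more factors by eigenvalue above one:

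| Loading | 20% | 30% | 50% | 70% |
|---|---|---|---|---|
| 0.6 | 100% | 98% | 80% | 53% |
| 0.7 | 87% | 54% | 8% | 1% |
| 0.8 | 23% | 1% | 0% | 0% |

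Repeat runs with new random draws agree (loading 0.6: 100/98/77–83/50–56%; loading 0.7: 87–88/50–53/8–9/0–1%). With factor correlation 0.4 the pattern holds: at loading 0.7, 19% with 60% zeros and 88% with 80% zeros. If three factors are true (correlation 0.6), four or more are kept in 96/83/51/26%, 65/29/2/0% and 6/0/0/0% at the three loadings.

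**Which sentence causes it.** With the elbow located by the acceleration factor, the scree count exceeded the eigenvalue count in 0 to 6.6% of samples, and in 0% in most cells.

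**Consequence for grouping.** Share with all 13 items in the right group by highest loading, under principal components with varimax (endorsement 20/30/50/70%):

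| Loading | Plan | Parallel-analysis count | Two factors fixed |
|---|---|---|---|
| 0.6 | 0/2/18/43% | 26/39/57/62% | 33/56/82/88% |
| 0.7 | 11/43/91/99% | 65/79/85/90% | 75/90/99/100% |
| 0.8 | 75/99/100/100% | 95/97/98/99% | 96/100/100/100% |

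Every sample with a spurious factor had items in wrong groups. At loading 0.7 with 20–50% endorsement, 40–49% of those samples had a factor holding only one or two items. Over-extraction did not raise the number of samples losing an item to the 0.50 cut; the harm is wrong grouping.

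**Does the CFA catch it?** Over-extracted models were fitted to a second half after the 0.50 cut, leaving out models with a one-item factor (60 fits per cell). RMSEA above 0.08 or CFI below 0.90 flagged 78% (loading 0.7, 20% endorsement), 42% (0.7, 30%) and 13% (0.6, 50%). In the first of these cells the true model also missed CFI 0.90 in 58%, so much of that flagging reflects floor-heavy items.

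**Would pre-stated models help?** BIC (chi-square + parameters × ln 150; 26, 27 and 29 parameters for the one-factor, 8+5 and 4+4+5 models; 200 data sets per cell) picks a true 8+5 in 90–100% of samples in every cell. It picks a true 4+4+5 in 65/75/91/91% at loading 0.6, 94/99/100/100% at 0.7 and 100% at 0.8.

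**The case against.** The strongest reply is that the outcome depends on quantities nobody knows yet. If loadings reach the 0.70 that the protocol prefers and half or more of the children score above 0, the plan's rule over-extracts in 8% or fewer and groups items correctly in 91–99%. At 0.8 with 30% or more it is essentially faultless. That stands, and it makes the point conditional.

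The CFA also runs on separate children with stated fit cut-offs. A reader might infer that any spurious factor passes straight into the construct-validity claim. The documents do not support that: the cut-offs can reject such a model. They miss it often enough, though, that they cannot serve as the only safeguard.

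A reader might also blame the scree sentence. It adds almost nothing to the count; the excess comes from the eigenvalue sentence.

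Finally, a reader might infer that section 4 and CIPN measurements contradict each other on who is asked the pain items, since section 4 says "If pediatric patients reported experiencing these symptoms, they were directed to answer four additional questions regarding painful numbness and tingling". They do not. Section 4 is describing the original form. The sentence on the 6-point scale under CIPN measurements gives the response format, not who is asked. That paragraph is silent on branching, and a 0–65 total fits a branched form. How an unasked item is scored is detail that an analysis plan not shown here may supply.

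**Conclusion.** The point holds in conditional form. The plan fixes a rule that can only add factors, at 150 children. Over-extraction is likely at loading 0.6 at every endorsement examined (53–100%) and at loading 0.7 with 30% or fewer scoring above 0 (54–87%). It is small at 0.7 with 50% or more (1–8%) and at 0.8 with 30% or more (0–1%); at 0.8 with 20% it is 23%. These figures rest on assumed equal loadings, endorsement and a factor correlation of 0.6, none of which the protocol states.

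The consequence is wrongly grouped items in the model handed to the CFA, detected there in some samples but not all, while two groupings already described in the protocol go unnamed as candidates. This is a worthwhile, inexpensive improvement. It does not call the sample size or the split-half design into question.

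**What to change.** **Factor analysis, EFA paragraph.** Stop letting eigenvalue above one decide. Use parallel analysis (95th percentile) read together with the scree plot, and report the one-, two- and three-factor solutions side by side, so that no single count settles the matter.

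**Factor analysis, CFA paragraph.** In the CFA half, on all 13 items before any deletion, fit the one-factor, 8+5 and 4+4+5 models beside the EFA-derived model. Compare the three pre-stated models by BIC and show the fit of all four.

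**Cost.** Wording, a short SPSS syntax for parallel analysis, and BIC from each model's chi-square and parameter count. No extra children or visits.

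**Downsides.** Parallel analysis over-extracts in at most 4% of the two-factor samples above, but on its own it can keep too few: one factor in 34–42% at loading 0.6 and 10–17% at 0.7, and in 78–92% if the factors correlate 0.8 at 30% endorsement. It finds a true third factor in at most about 50%. At loading 0.7 with 50–70% endorsement it groups items slightly worse than the plan (85/90% against 91/99%), and at 0.8 with 30% or more nothing is gained. That is why it should not decide alone and why the pre-stated models are needed. Fitting them before deletion matters because, at 30% endorsement, the 0.50 cut removes at least one item in 82/45/2% of samples under the plan and 97/49/2% with the parallel-analysis count (loadings 0.6/0.7/0.8). BIC has limits too: with factors correlating 0.8 and 30% endorsement it picks a true 8+5 in 74/94/98%, so all fits should be shown. None of this removes the misfit that maximum likelihood produces on items with very many zeros.
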